4.10. Qualitative study involving patients and surgeons

Our 12 month pilot study will include a qualitative component to highlight any barriers or facilitators to recruitment and retention of trial participants. This will inform any improvements that can be made to the recruitment process and how the trial is communicated to potential participants in the full trial. There will be two components: (i) interviews will be conducted with patients who agree to take part in the trial (n=15-20) and who decline participation (n=5-10); (ii) interviews with participating surgeons and trial recruiters regarding their preferences and views on the trial (n=15-20). We will also seek permission from the patient and trial recruitment teams to audio-record recruitment consultations where feasible. This will be on a voluntary basis. Implicit consent will be taken from trial recruitment teams by the return of completed recordings. Recruitment teams will be asked to obtain verbal consent from patients to audio-record consultations. A selection of consultation recordings (from those declining and accepting participation) will be analysed thematically in order to identify improvements in communication regarding how best to explain randomisation and the different care pathways [44].

4.10.1. Data collection: qualitative study

We will undertake semi-structured interviews with people who agree to take part in the trial including patients from both treatment options, and those who decline participation. A flexible interview schedule will be developed following discussions with the research team, PPI

members and surgeons with expertise in this area. Interviews will be conducted face-to-face, telephone or Skype according to the preferences of each interviewee. All interviews will be recorded with permission. These interviews will explore patients' responses to the invitation to join the trial; their experiences of the trial processes; and reasons for participation/non-participation. Patient interviewees will be purposefully sampled to ensure maximum variation from the cohort of interviewees who are eligible for recruitment into the trial and will be based on age, gender and responses to the quantitative questions relating to treatment preferences and reasons for non-consent into the trial. In addition, we will carry out interviews with participating surgeons and trial recruiters from across all of the participating centres regarding their preferences and views on the trial, the barriers and facilitators to offering these interventions and willingness to randomise. We will interview participants until no further conceptual categories emerge, therefore we have provided for some flexibility in the sample size, however, this number is consistent with recommendations [45].

Interviews with patients will be conducted as soon as possible after the invitation to participate in the study to discuss in more detail the participants' experiences of making the decision to enrol/decline; trial procedures; the intervention they were given; and their recovery. We will specifically ascertain how the participants felt about the randomisation process and to provide feedback on the information they were given and what (if any) information was missing – for example, information pertaining to their immediate recovery etc.

5. Data management

Study data will be recorded in a number of files for both the administration of the study and collection of patient data. All data will be completely anonymised for purposes of analysis and any subsequent reports or publications. For the purposes of ongoing data management, once randomised, individual patients will only be identified by trial numbers.

For the qualitative interviews, all participants will be assigned a unique ID so as to maintain anonymity. Recordings and transcripts will be anonymised and stored on a password-protected computer for three years following completion of the study. Only the research team will have access to qualitative data. Consent forms will be kept in a locked filing cabinet, separate to the other data collected for the study. Transfer of data to any external transcriber will be via the University based secure web-based data transfer system.

5.1. Data entry

The data collected by sites using paper CRFs, will be mailed (original paper CRFs) to YTU to be entered/scanned into a secure web-based interface, specifically developed for this study. When necessary, a site can securely return the CRF electronically.

The staff involved in the trial (both at the sites and YTU) will receive training on data protection. The staff will be monitored to ensure compliance with privacy standards.

Data will be checked according to procedures detailed in the trial specific Data Management Plan.

5.2. Data storage

Each site will hold data according to the Data Protection Act 1998 and data will be collated in CRFs identified by a unique identification number (i.e. the Trial number) only. A Trial Enrolment Log at the sites will list the ID numbers. YTU will maintain a list of trial numbers for all trial patients at each site.

All YTU data recorded electronically will be held in a secure environment with permissions for access as detailed in the delegation log. The Department of Health Sciences, in which YTU is based at the University of York, has a backup procedure approved by auditors for disaster recovery. Full data backups are performed nightly using rotational tapes, to provide five years' worth of recoverable data. The tape backup sessions are encrypted and password protected, with tapes stored in a locked fire-proof safe in a separate secured and alarmed location. All study files will be stored in accordance with Good Clinical Practice guidelines. Study documents (paper and electronic) held at the YTU will be retained in a secure (kept locked when not in use) location for the duration of the trial. All essential documents, including source documents, will be retained for a minimum period of five years after study completion. The separate archival of electronic data will performed at the end of the trial, to safeguard the data for the period(s) established by relevant regulatory requirements. All work will be conducted following the of University York's data protection policy which is publically available (www.york.ac.uk/records-management/dp/policy).

5.2.1. Proposed time period for retention of relevant trial documentation

Essential trial documentation will be kept with the Trial Master File and Investigator Site Files. The Sponsor will ensure that this documentation will be retained for a minimum of five years after the conclusion of the trial to comply with standards of Good Clinical Practice. Case Report

Forms will be will be stored up to 10 years after the conclusion of the trial as paper records; and a minimum of 20 years in electronic format in accordance with guidelines on Good Research Practice [46]. All paper records will be stored in a secure storage facility at York Trials Unit or in the longer term transferred to a secure off-site storage facility. All electronic records will be stored on a password protected server. For the qualitative interviews, recordings and transcripts will be anonymised and kept in a locked office for three years following the completion of the study.

5.3. Quality Assurance and Quality Control

Hull and East Yorkshire NHS Trust is the lead sponsor for this project and takes overall responsibility for the quality of study conduct. This study will be fully compliant with the Research Governance Framework and MRC Good Clinical Practice Guidance. A trial specific data management plan agreed by the Chief Investigator, Sponsor, YTU and other study investigators will be drafted to provide detailed instructions and guidance relevant to database set up, data entry, validation, review, query generation and resolution, quality control processes involving data access and transfer of data to the sponsor at the end of the study and archiving.

A rigorous programme of quality control will be undertaken. The day-to-day management of the trial will be the responsibility of the Trial Co-ordinator based at York Trials Unit. Regular meetings with the Trial Management Group will be held and the trial team will monitor adherence to the trial protocols at the trial sites. Quality assurance checks will be undertaken by York Trials Unit to ensure integrity of randomisation, study entry procedures and data collection.

5.4. Statistical methods

5.4.1. Statistical Analysis Plan

Full analyses will be detailed in a statistical analysis plan (SAP), which will be finalised prior to the end of data collection and which will be reviewed and approved by the independent data monitoring committee. Any exploratory analyses of sub-groups that are of clinical interest will be pre-specified in the SAP. This trial will be reported according to the CONSORT guidelines for clinical trials (Consolidated Standards Of Reporting Trials statement).

5.4.2. Internal pilot

The recruitment rate and 95% confidence interval (CI) will be estimated from the data collected. A CONSORT diagram will be constructed to show the flow of participants through the study

and the following outcomes calculated: number of eligible patients; proportion of eligible patients approached for consent; proportion of eligible patients not approached and reasons why; proportion of patients approached who provide consent; proportion of patients approached who do not provide consent; proportion of patients providing consent who are randomised; proportion of patients randomised who do not receive the randomly allocated treatment; proportion of patients dropping out between randomisation and follow-up. Data will be summarised on the reasons why eligible patients were not approached, reasons for patients declining to participate in the study; reasons why randomised patients did not receive their allocated treatment and reasons for drop-out, if available. Results will be compared against the study's recruitment assumptions and progression targets, and continuation of the trial or relevant modifications will be decided by the funding body.

5.4.3. Statistical analysis - main trial

A CONSORT flow diagram will be provided to display the flow of participants through the study (see Figure 2). The number of participants withdrawing from the trial will be summarised with reasons where available. Baseline characteristics will be presented by trial arm both for the trial population as randomised and for those patients for whom primary outcome data was available at 12 months follow-up. Statistical analyses will be on intention to treat (ITT) basis with patients being analysed in the groups to which they were randomised. Statistical significance will be at the 5% level, and analyses will be conducted in the latest available version of Stata or similar statistical software. All trial outcomes will be reported descriptively by trial arm at all time points at which they were collected. Continuous PROMS data will be summarised as means, standard deviations, medians and ranges, whereas data on further procedures and complications will be summarised as frequencies and percentages. Outcomes will be illustrated graphically over time where appropriate, including confidence intervals.

The primary analysis model will be a mixed effects regression analysis, with DRI scores at 3, 6 and 12 months follow-up as the dependent variable, adjusting for baseline DRI, randomised treatment arm and other pertinent baseline characteristics as fixed effects and including treating centre and surgeon as random effects. We will consider adjusting on fracture type and baseline DRI; however we will first monitor how well fracture type and baseline DRI are collected during the pilot phase to determine whether these adjustments are feasible. The model will account for similarities of scores by the same person by means of an appropriate covariance structure. The estimated treatment group differences at 12 months will be reported as the primary endpoint with 95% confidence interval and associated p-value. Secondary analyses of

the primary outcome will include an estimate of treatment group differences at 3 and 6 months from the same model. A separate model additionally including 24 month data will derive treatment group differences at that point. The overall treatment effect across all prior time points will be derived at 12 and 24 months (equivalent to area under the curve estimates).

The amount of missing data will be mitigated by including 3, 6 and 12 month data in the primary analysis model, which allows the inclusion of any patient with complete baseline data and valid outcome data at one or more follow-up points. The nature of missingness for outcome data will be explored and multiple imputation and/or deviations from the missing-at-random assumption considered if appropriate.

There will be two exploratory subgroup analyses of the primary outcome, to assess the effectiveness of the different treatments across different patient subgroups. One will consider the impact of baseline patient preferences, whereby an interaction between treatment arm and patient preference (receipt of preferred treatment, non-preferred treatment, no prior preference) will be added to the primary analysis model. The other will consider fracture types (C1+C2 vs C3), whereby an interaction between treatment arm and fracture type will be added into the primary analysis model. These interactions will be presented graphically, and the p-value of the interaction will be reported. While there is insufficient statistical power for these interactions, they may help inform further research.

We will consider the impact that time to surgery has on the primary outcome by reporting DRI scores descriptively for the four patient groups formed by considering treatment allocation together with time to surgery (early (within 36 hours) Vs. late).

Secondary continuous PROMS outcomes will be analysed by similar mixed effects regression analyses to the primary analysis model. Binary secondary outcomes of additional procedures and complications will be analysed by mixed effects logistics regression analyses.

Figure 2: ACTIVE Trial CONSORT flow diagram Inclusion criteria: Patients with closed Type C Exclusion criteria: Pilon fractures of the distal Prior failed fixation; Aged ≥16 years; tibia identified (AO 43 - C1, Pathologic fracture; With closed pilon fractures, C2 and C3) by member of classified AO 43- C which can be bi-Patient unable to understand lateral and patients with polytrauma; research team and recorded instructions for treatment on the screening log > 21 days since injury Where the treating surgeon believes the patient will benefit from surgical Pre-existing skin condition which precludes open surgery fixation. Not eligible Eligible Study set up & internal pilot Phase 1: 0-18 months Patient has capacity - obtain consent Patient lacks capacity (e.g. temporary cognitive impairment), approach consultee No consent Consultee declines Consent - Baseline Consultee agrees DRI, OMAS Randomise EQ-5D-5L Patient preferences Main recruitment, follow up to primary end point I year, main HTA report and Internal plate fixation (167 External fine wire fixation (167 patients) patients) Received allocated intervention (n=) Received allocated intervention (n=) Did not receive allocated intervention Did not receive allocated intervention (n & reasons) (n &reasons) Perioperative data collected Perioperative data collected Use of physiotherapy recorded Use of physiotherapy recorded Approach patient when regains capacity 3 months after randomisation Qualitative study: If consents: (12-month pilot phase) Outcome measures as at baseline, resource use and loss Collect EQ-5D-5L to follow-up Up to 30 patients who either If declines: Participant consent (n=15-20) or do not withdrawn as postconsent (n=5-10) to the 6 months after randomisation randomisation ineligible main trial. Outcome measures as at baseline, resource use and loss to follow-up 15-20 participating surgeons and trial recruiters 12 months after randomisation Outcome measures as at baseline, resource use and loss to follow-up Phase 2: 19-92 months 24 months (2/3rds sample) after randomisation Outcome measures as at baseline, resource use and loss Abbreviations to follow-up

Analysis

Draft HTA Report; dissemination

dissemination

index

DRI – Disability rating

OMAS - Olerud and

Molander Ankle Score EQ-5D-5L - EuroQoL 5 dimension 5 level

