4.2.1. Inclusion criteria

- Patients aged 16 years or older
- With a closed intraarticular pilon fracture of the distal tibia classified according to AO: AO
 43 Cl, C2 and C3 (complete articular). This includes patients with a bi-lateral pilon fracture and who have polytrauma.
- Where the treating surgeon believes the patient will benefit from surgical fixation

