4.4. Outcomes

4.4.1. Primary outcome

The primary outcome is the Disability Rating Index (DRI) at 12 months post-randomisation. The DRI is a validated patient-reported outcome measure questionnaire [32]. It consists of a 12-item

Visual Analogue Scale questionnaire assessing the patients' own rating of their disability specifically related to the lower limb. This data will be collected at baseline, 3, 6, 12 and 24 months follow-up post-randomisation. The DRI has been proven to be a robust, practical clinical and research instrument with good responsiveness and acceptability for assessment of disability caused by impairment in the lower limb. Baseline assessment will ask participants about their functioning *before* their injury and *before* their surgery.

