4.5. Sample size

The primary outcome is the DRI. In order to detect a minimum clinically important difference of 8 points on the DRI (SD 20) [32, 39, 40] with 90% power and 5% statistical significance, 133 participants per group are required (calculated using nQuery). Accounting for 20% attrition at the primary endpoint of one year follow-up, the total recruitment target is 334 participants (167 per arm). Not all participants will be followed up at the 24 month time-point. Assuming two thirds of patients included in the primary analysis are followed up to two years, statistical power will be 75% for the group comparison at two years.

On 6th September 2021, the funder approved a request from the study team for a costed extension, with the proviso that the sample size be recalculated to provide 80% power. In order to detect a minimum clinically important difference of 8 points on the DRI (SD 20) with 80% power and 5% statistical significance, 100 participants per group are required. Accounting for 20% attrition at the primary endpoint of one year follow-up, the total recruitment target is 250 participants (125 per arm). An implication of the costed extension is that a higher proportion of patients will be followed up at the 24 month time-point. Assuming 80% of patients included in

the primary analysis model are followed up for the revised target, statistical power will be 71% for the group comparison at two years. Recruitment will continue beyond the target of 250 patients if that is met until the end of the recruitment period on 31st October 2023.

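### Protocol 5.4.3 both fixes baseline DRI in the primary model and makes it conditional on pilot data collection, so poor collection would drop the covariate or exclude randomised patients

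*Protocol*

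**What the plan says.** All the relevant text on the model is in Protocol section 5.4.3.

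- The primary model is a mixed effects regression of DRI at 3, 6 and 12 months, "adjusting for baseline DRI, randomised treatment arm and other pertinent baseline characteristics as fixed effects", with centre and surgeon as random effects.
- The next sentence reads "We will consider adjusting on fracture type and baseline DRI; however we will first monitor how well fracture type and baseline DRI are collected", and gives the purpose of that monitoring: "during the pilot phase to determine whether these adjustments are feasible". No completeness threshold is stated, and no result of the check is reported.
- On missing data, the section says that using all three time points "allows the inclusion of any patient with complete baseline data and valid outcome data at one or more follow-up points". The provision for multiple imputation that follows concerns outcome data only.
- For the exploratory comparison of C1+C2 with C3, "an interaction between treatment arm and fracture type will be added into the primary analysis model".

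Three other sections bear on this. Section 4.4.1 describes the baseline DRI: "Baseline assessment will ask participants about their functioning" before the injury and before surgery. Section 4.2.1 admits patients "With a closed intraarticular pilon fracture of the distal tibia classified according to AO" as C1, C2 or C3. Section 4.5 sets the revised size to "detect a minimum clinically important difference of 8 points on the DRI (SD 20) with 80% power and 5% statistical significance", giving 100 per group.

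**The concern.** Consecutive sentences give baseline DRI two statuses: a term in the model, and a term that may be left out. An analyst who follows one departs from the other.

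The condition is also a poor rule. In a randomised trial, incomplete collection does not force a choice between dropping a baseline covariate and losing patients. Missing baseline values can be filled by a simple rule that ignores allocation, and everyone stays in. The protocol offers no such rule, and its entry condition for the model points to complete cases. If collection was poor, one branch discards a collected and possibly prognostic variable. The other removes randomised patients from an analysis that the same section calls intention to treat.

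Missing baseline DRI is foreseeable. Section 7.2.2 allows entry through a consultee. For patients who regain capacity, section 4.4.2 and Figure 2 provide for late collection of the EQ-5D-5L, with no equivalent stated for the DRI.

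**Working it through.** **Inputs.** Difference 8, SD 20, 5% significance (taken as two-sided; the protocol does not say), 100 per group, 20% attrition: Protocol 4.5. The correlation r of the covariates with 12-month DRI, and the share of variance R² = r² that they explain, are not given, so a range is assumed. The check treats the 12-month comparison as a two-sample comparison of means, as section 4.5 does, and ignores the repeated measures and the random effects.

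**Step 1: reproduce the plan's figures.** With the noncentral t distribution and no covariate, 80% power needs 100 per group and 90% power needs 133. Allowing for attrition, 100/0.8 = 125 per arm (250 in total), and 133/0.8 = 166.25, rounded up to 167 per arm (334 in total). All match section 4.5. The power at 100 per group is 80.4% (80.7% by the normal approximation). The stated size therefore takes no credit for adjustment.

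**Step 2: what adjustment could add.** Residual SD = 20 × √(1 − R²). The standardised signal is 8 / (residual SD × √(2/100)), and normal-approximation power is Φ(signal − 1.96).

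| R² (assumed) | Residual SD | Signal | Power, normal | Power, t |
|---|---|---|---|---|
| 0 | 20.00 | 2.828 | 80.7% | 80.4% |
| 0.01 | 19.90 | 2.843 | 81.1% | 80.8% |
| 0.05 | 19.49 | 2.902 | 82.7% | 82.3% |
| 0.10 | 18.97 | 2.981 | 84.7% | 84.3% |
| 0.15 | 18.44 | 3.068 | 86.6% | 86.3% |

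The gain runs from about 0.4 points at R² = 0.01 (r = 0.1) to about 6 points at R² = 0.15.

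**Step 3: what complete-case adjustment costs.** If a fraction m of patients lacks baseline data, the information relative to an unadjusted analysis of everyone is (1 − m)/(1 − r²). It falls below 1 when m exceeds r². Break-even missingness is therefore 4% at r = 0.2, 9% at r = 0.3 and 25% at r = 0.5. By the t calculation, against 80.4% unadjusted:

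- r = 0.2 with 5% missing (95 per group): 79.9%
- r = 0.3 with 10% missing (90 per group): 79.9%
- r = 0.2 with 10% missing (90 per group): 77.8%

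**Step 4: filling instead of excluding.** Suppose missing baseline values are replaced by a constant without regard to arm, and missingness is unrelated to the values. The explained share is then roughly R²(1 − m) and nobody is lost. With R² = 0.10 and m = 10%, that is 0.10 × 0.90 = 0.09. Power at 100 per group is 83.9%, against 80.3% for complete cases at 90 per group.

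**The case against.** The strongest reply is that section 5.4.1 leaves the full analysis to a SAP approved by the independent data monitoring committee, and that covariates and missing baseline values are commonly settled there. That stands as far as later resolution goes: the SAP is not at hand, and the absence of a reported pilot decision cannot be held against the protocol. It does not remove two conflicting sentences in the protocol, or an entry condition that points to complete cases.

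A second reply is that checking feasibility was sensible, because complete-case adjustment can cost power. Step 3 confirms this. It is a reason to change how missing baseline values are handled, not to make the covariate optional.

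The objection is right on several stronger readings that a reader might infer:

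- **Planned power in danger.** It is not. The 80% rests on the unadjusted SD.
- **An assured precision gain.** No correlation is given, and a rating of function before the injury may predict function a year after a severe fracture only weakly.
- **A model chosen on results.** The stated trigger is data collection in the pilot (months 7 to 18, section 8), not outcomes by arm. Section 4.7.1 also keeps staff analysing questionnaires blind to allocation.
- **A contradiction on fracture type.** It is nowhere named as a firm covariate, so its status is conditional but consistent. Section 4.2.1 requires only type C, so eligibility does not itself guarantee a recorded subtype, although section 4.8.1 plans to collect subtype numbers.
- **A subgroup model without its main effect.** Nothing says that the main effect would be omitted. Adding an interaction is ordinary shorthand, used in the same way for patient preference.

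**Conclusion.** The point holds in limited form. The protocol contradicts itself on whether baseline DRI is in the primary model. Combined with the complete-baseline entry condition, its text leaves two poor outcomes if collection fell short: dropping the covariate, or losing randomised patients.

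What is at stake is those patients, plus precision that was never counted: about 83%, 85% or 87% power in place of about 81% (normal approximation) if R² is 5%, 10% or 15%, and next to nothing if pre-injury DRI predicts weakly. Every R² and r here is an assumption. The stated 80% power stands either way.

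This is an improvement available at almost no cost, together with a wording conflict on baseline DRI that should be reconciled. It is not a flaw that threatens the validity of the primary comparison.

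**What to change.** In Protocol 5.4.3, and in the SAP to match:

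1. Delete the sentence that only considers adjustment.
2. State that the primary model includes baseline DRI obtained before randomisation and fracture type (C1+C2 v C3) as fixed effects, irrespective of completeness.
3. Fill missing baseline DRI with the overall mean, and missing fracture type with a 'not classified' category, both without regard to arm. Treat a DRI not obtained before randomisation as missing, so that recall after a known allocation does not enter as a covariate.
4. Replace the complete-baseline condition so that every randomised patient with at least one follow-up DRI is included.

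The cost is an edit to the protocol and SAP. Section 4.4.1 already schedules baseline DRI and section 4.8.1 already plans subtype data, so no further patients, visits or data items are needed.
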